For all enrolled subjects who undergo the ablation procedure, the subjects will be treated with the commercial Rhythmia HDx System with commercially available Software Version 2.0 with DirectSense technology (or any commercially available updates that are released during the course of the study); the IntellaMap Orion mapping catheter and the IntellaNav MiFi OI ablation catheter.

Follow-up Schedule

Each subject undergoing PVI will be followed at index procedure, at predischarge visit, at the month 3 assessment and at month 4 follow up. The visit at three months after index procedure will include an invasive evaluation with the Rhythmia Mapping system to evaluate residual conduction gaps after PVI. The study will be considered complete after all enrolled subjects have completed the month 4 follow up.

Data Collection Overview

Data Collected	ENROLLMENT/ BASELINE	INDEX PROCEDURE (Day 0)	PRE-DISCHARGE (0-7 days post procedure)	MONTH 3 FOLLOW UP (90±21 days)	MONTH 4 FOLLOW UP (120± 30 days)	ADDITIONAL PROCEDURE (if applicable)	ADDITIONAL VISIT (if applicable)
Informed Consent	X						
Inclusion/Exclusion	X						
Demographic data	X						
Medical History	X						
Medication Regimen	X	X*	X*	X*		X*	
Mapping and procedure data		X		X		X**	
Patient status	X	X		X	X	X	
Protocol Deviations	X	X	X	X	X	X	X
Adverse Event/ Device Deficiency Reporting***	X	X	X	X	X	X	X
			•				

Oupling Information From The Rhythmia TM HDx Mapping DireCtSense TM Technology In The Treatment Of Paroxysmal ation- A Non-RandomiZed, ProspEctive Study (LOCALIZE)
*Medication changes only will be captured **If additional procedure includes an additional ablation procedure in the LA with Rhythmia HDx mapping system, IntellaMap Orion mapping catheter and IntellaNav MiFi OI ablation catheter. *** For details on Adverse Event and Device Deficiency reporting, please refer to Section 20.
Enrollment is expected to be completed in approximately 6 months; therefore the total study duration is estimated to be approximately 10 months.
• History of recurrent symptomatic PAF with ≥1 episode reported and documented within the 365 days prior to enrollment; PAF is defined as AF episodes that last ≥30 seconds in duration and terminate within 7 days.
 Refractory or intolerant to at least one Beta Blocker, Calcium Channel Blocker, Class I OR Class III anti-arrhythmic drug (AAD);

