8.1. Scale and Duration

Enrollment will be considered as complete when 60 patients undergo the index ablation procedure and complete encircling of the 4 PVs (2 PV pairs). Up to 6 sites in EU may participate in the study. To reduce the impact of individual center bias, each site may perform up to 30 index ablation procedures. This limit of 30 procedures cannot be exceeded, unless Boston Scientific gives written approval to do so.

[figure not shown]
Each treated subject will be followed for 4 months after the index ablation procedure (index procedure); therefore treated subjects will be followed at index procedure, at pre-discharge visit, at the month 3 assessment and at month 4 follow up.

The study will be considered complete upon completion of the final month 4 follow-up.

A study subject's participation will be considered complete when all protocol required visits have been completed.

It is anticipated that enrollment will be conducted over a period of 6 months; therefore the total study duration is estimated to be 10 months.

Figure 8.1-1: LOCALIZE Study Design

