A subject who signs informed consent, meets eligibility criteria and had the encircling of the 4 PVs started (post the 1st RF application in the left atrium), but did not have the initial encircling for all 4 PVs (2 PV pairs) completed will be classified as "ATTEMPT". Attempt subjects will be followed up until Pre-Discharge. A subject ID is created by Medidata Rave upon entering the subject in the eCRF. For Attempt subjects, all applicable case report forms must be completed. If applicable, an Adverse Event eCRF form must be completed. Attempt subjects do not count towards the enrollment ceiling and will not be used for analyses of the endpoints. The original signed Informed Consent must be maintained in the center's patient file.

Treatment

A subject who had encircling of the 4 PVs (2 PV pairs) completed will be classified as "TREATMENT". These subjects are followed in accordance with the follow-up schedule and included in all study analyses. A subject ID is created by Medidata Rave upon entering the subject in the eCRF. For Treatment subjects, all applicable case report forms per the protocol must be completed. Treatment subjects do count towards the enrollment ceiling and will be used for analyses of the endpoints. The original signed Informed Consent and any relevant documentation must be maintained in the center's patient file.

It is the investigational sites's responsibility to list all Consent Ineligible, Intent, Attempt and Treatment subjects on the Screening and Enrollment Log.

11. Study Methods

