11.6. Pre-discharge visits

The pre-discharge follow up visit should be done before hospital discharge but no later than 8 days past index ablation procedure, even if the subject has to remain at the hospital for a longer time (e.g. due to an Adverse Event).

The data collection at Pre-Discharge includes:

- Date of visit;
- Rhythm at time of pre-discharge;
- Variations in current medication regimen;
- Reportable Adverse Events, if applicable
- Additional Follow Ups/Procedures, if applicable

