20.4. Investigator Reporting Requirements

The communication requirements for reporting to BSC are as shown in Table 20.4-1

Adverse events and device deficiencies must always be reported through the eCRF system. However, in the event that an alternative method of reporting is necessary (i.e. the eCRF system is unavailable), please report the adverse event or device deficiency to Boston Scientific by sending the Event Notification Form via email to the following email address:

[contact]

Table 20.4-1: Investigator Reporting Requirements

Event Classification	Communication Method	Communication Timeline post-market studies* (MEDDEV 2.12/2: GUIDELINES ON A MEDICAL DEVICE VIGILANCE SYSTEM)
Unanticipated Adverse Device Effect / Unanticipated Serious Adverse Device Effect	Complete AE eCRF page with all available new and updated information.	 Within 1 business day of first becoming aware of the event. Terminating at the end of the study
Serious Adverse Event	Complete AE eCRF page with all available new and updated information.	 Within 10 business days after becoming aware of the event or as per local/regional regulations. For deaths, within 3 calendar days of site notification Reporting required through the end of the study
	Provide all relevant source documentation (unidentified) for reported event upon request of the sponsor	When documentation is available
Serious Adverse Device Effects	Complete AE eCRF page with all available new and updated information.	 Within 2 business days of first becoming aware of the event or as per local/regional regulations. Reporting required through the end of the study
	Provide all relevant	When documentation is available

Event Classification	Communication Method	Communication Timeline post-market studies* (MEDDEV 2.12/2: GUIDELINES ON A MEDICAL DEVICE VIGILANCE SYSTEM)
	source documentation (unidentified) for reported event upon request of the sponsor.	
Device Deficiencies (including but not limited to failures, malfunctions, and product nonconformities) Note: Any Investigational Device Deficiency that might have led to a serious adverse event if a) suitable action had not been taken or b) intervention had not been made or c) if circumstances had been less fortunate is considered a reportable event.	Complete Device Deficiency eCRF with all available new and updated information.	Within 2 business days of first becoming aware of the event. Reporting required through the end of the study

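### Attempt subjects have had left-atrial RF but no scheduled contact after pre-discharge, while the synopsis and section 20 imply observation or reporting for longer

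*Combined protocol and SAP*

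**What the plan says.** Section 10.3 defines an Attempt subject as an eligible, consented subject who "had the encircling of the 4 PVs started (post the 1st RF application in the left atrium), but did not have the initial encircling" of all four veins completed. For this class it says "Attempt subjects will be followed up until Pre-Discharge" and "Attempt subjects do not count towards the enrollment ceiling and will not be used for analyses of the endpoints". All applicable case report forms are still required, including an adverse-event form where relevant.

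Table 11.1-1 places the pre-discharge visit at 0 to 7 days; section 11.6 allows it "no later than 8 days past index ablation procedure".

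Other passages describe follow-up differently:

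- Synopsis, in the row on visits: "Each subject undergoing PVI will be followed at index procedure, at predischarge visit, at the month 3 assessment and at month 4 follow up".
- Synopsis, same row: "The study will be considered complete after all enrolled subjects have completed the month 4 follow up".
- Section 8.1: "Each treated subject will be followed for 4 months after the index ablation procedure (index procedure").
- Sections 11.1 and 11.11: the schedule to month 4 applies to Treatment subjects.
- Section 20.4, for serious and non-serious events, serious device effects and device deficiencies: "Reporting required through the end of the study". Section 20.1 likewise makes a procedure-related new arrhythmia reportable from the index procedure to the end of study.

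Section 12.2.1 plans additional analyses in all enrolled subjects, overall and by the section 10.3 categories. Section 20.1 promises routine aggregate safety reviews.

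**The concern.** For adverse events, a subject becomes at risk through left-atrial RF, not through completion of the circle. An Attempt subject has been exposed, yet scheduled observation stops within about a week. Section 19.3 lets the physician interrupt a procedure when risk to the subject is expected. That is one documented way of becoming an Attempt subject, so the class need not be a random sample of those ablated.

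What is at stake is the descriptive adverse-event and device-event reporting. Attempt counts from about a week would stand beside Treatment counts from about four months, and no rule says how long an RF-exposed subject is under observation. Section 11.8 also asks whether a repeat left-atrial ablation followed an incomplete index procedure. That question fits Attempt subjects directly, but their follow-up ends before most such procedures could be recorded.

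**Working it through.** The plan states no safety rate, safety sample size or expected number of Attempt subjects, so there is no figure to reproduce. The check has three steps.

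**1. The passages side by side, for a subject with RF started and encircling incomplete**

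| Place | Observation or reporting implied |
|---|---|
| 10.3 | To pre-discharge |
| 11.1, 11.11 | Month 4 for the Treatment class only; agrees with 10.3 |
| Synopsis, subjects undergoing PVI | Month 4, if a started PVI counts as undergoing PVI |
| Synopsis, study completion | Month 4 for all enrolled; loose wording (see the objection) |
| 8.1 | Ambiguous: treated could mean anyone ablated or the Treatment class |
| 20.1, 20.4 | Reporting to the end of study, no exception by class |

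The clear disagreement is between 10.3 and the synopsis sentence on subjects undergoing PVI. Section 20 adds a practical gap: it sets a reporting duty without a visit at which the site would learn of the event.

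**2. Share of the follow-up period with scheduled observation**

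Inputs: last Attempt visit on day 7 (Table 11.1-1) or day 8 (11.6); month 4 at day 120, window day 90 to day 150 (11.1).

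- Share covered = last visit day / month 4 day. Nominal: 8/120 = 6.7%, or 7/120 = 5.8%.
- Range over the windows: 7/150 = 4.7% to 8/90 = 8.9%.
- Days without scheduled contact: 90 − 8 = 82 to 150 − 7 = 143; nominal 120 − 8 = 112, which is 112/120 = 93%.

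**3. What could be missed, under stated assumptions**

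Let k be the number of Attempt subjects, in addition to the 60 Treatment subjects, and p the probability that an Attempt subject has a reportable event after pre-discharge. Neither is in the documents. The ranges below are assumptions, subjects are taken as independent, and no event is assumed to reach the sponsor by another route.

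- Share of RF-exposed subjects = k/(60 + k)
- Expected affected subjects missed = k × p
- Probability of missing at least one = 1 − (1 − p)^k

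| k | Share of exposed | Expected missed, p = 2% to 20% | Probability of missing at least one |
|---|---|---|---|
| 1 | 1.6% | 0.02 to 0.20 | 2% to 20% |
| 3 | 4.8% | 0.06 to 0.60 | 6% to 49% |
| 6 | 9.1% | 0.12 to 1.2 | 11% to 74% |
| 9 | 13.0% | 0.18 to 1.8 | 17% to 87% |

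For example, with k = 3 and p = 0.20: 1 − 0.80³ = 0.488.

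**The case against.** The strongest reply is that the operative text is consistent: 10.3 gives an explicit rule for Attempt subjects, and 11.1 and 11.11 reserve month 4 for Treatment subjects. On this view only one synopsis sentence is out of line. Read literally, that sentence would also send Attempt subjects to the invasive month 3 remap of a circle that was never completed. This stands as a reason not to describe the whole protocol as contradicting 10.3. It does not remove the disagreement with the synopsis.

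A reader might take the synopsis completion rule as a second firm contradiction. It will not bear that weight. Section 10.1 makes anyone eligible and consented enrolled, so the rule would also cover Intent subjects, for whom 10.3 sets no follow-up.

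On section 20, if the duty covers Attempt subjects, events that sites learn of will be reported, so it goes too far to say that later events are not counted. If the end of study means the subject's own exit, there is no conflict. Both points are fair. What remains is that the text does not say which meaning applies, and no contact is scheduled in either case.

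Finally, there is no safety endpoint or safety hypothesis, the devices are marketed, and 12.2.1 already allows analyses by category. That limits the importance of the point. It does not supply the missing observation.

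**Conclusion.** The point holds as a gap in adverse-event ascertainment and an inconsistency to be reconciled. For RF-exposed Attempt subjects, scheduled observation ends by day 7 or 8, against day 90 to 150 for Treatment subjects. Events after that can be reportable under section 20 with nothing planned to detect them. The counts in this class are therefore complete or too low, never too high.

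The size is unknown. It is nil if no Attempt subjects occur or if sites report fully under section 20. The primary endpoint, the 60 Treatment subjects and the 50 with usable data do not change.

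Three stronger inferences are not supported:

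- A reader might conclude that the safety results will be biased downward. The documents define no safety estimate, and they do not show that any event would be missed.
- The 93% is calendar time per subject, not a share of events. Month 4 is also an imperfect comparator, because Treatment subjects have an invasive month 3 procedure that Attempt subjects do not.
- A reader might take Attempt to mean a failed procedure. Section 10.3 says only that initial encircling was not completed, and gives no reason.

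**What to change.** 1. Reconcile the synopsis Follow-up Schedule with sections 8.1, 10.3, 11.1, 11.11, 20.1 and 20.4. Say whether the words treated and undergoing PVI include Attempt subjects, and whether the end of study in section 20 means the end for the subject or for the whole study.
2. State one adverse-event observation period that covers every subject with at least one left-atrial RF application.
3. For Attempt subjects, collect adverse events after pre-discharge by a non-invasive contact. The Additional Visit form in 11.7 already allows a telephone visit and records reportable events. No month 3 remap is needed for this purpose.
4. Add to section 12 a summary of adverse events in Attempt plus Treatment, overall and by class, with observation time shown, so that unequal follow-up is visible.

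The cost is a few sentences of text and a small amount of site work for what are likely to be few subjects. Sample size and endpoint analyses stay as they are.

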11.1. Data Collection

Each Treatment subject will be followed at index procedure, at pre-discharge visit, at the month 3 assessment and at month 4 follow up. In order to reliably capture subject status at study end, the month 4 follow up has to be scheduled within 120 ± 30 days following the index procedure. If the subject needs to undergo an additional ablation procedure in the LA during the follow up period and the Rhythmia HDx mapping system, the IntellaMap Orion mapping catheter and the IntellaNav MiFi OI ablation catheter were used for this procedure, then this additional ablation procedure will be considered as the month 3 assessment if the month 3 assessment was not yet performed. No Protocol Deviation will have to be completed for a Visit Out Of Window. In case a different mapping system was used and/or different mapping and/or therapeutic catheters will be used for this additional ablation procedure in the LA, the subject will have to be withdrawn prior to this additional ablation procedure.

Table 11.1-1 provides an overview of the data to be collected at each visit.

INDEX PROCEDURE ADDITIONAL VISIT MONTH 3 FOLLOW **MONTH 4 FOLLOW** PRE-DISCHARGE PROCEDURE (if applicable) **UP** (120± 30 days) **ENROLLMENT/** (0-7 days post procedure) ADDITIONAL (90±21 days) (if applicable) (Day 0) **Data Collected** X Informed Consent Inclusion/Exclusion X X Demographic data Medical History X X X* X* X* X* Medication Regimen Mapping and procedure data X X X** X X Patient status Χ X X X X X X X X X **Protocol Deviations** Adverse Event/ Device X X X X X X X Deficiency Reporting***

Table 11.1-1: Data Collection Schedule

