10.2. Withdrawal

All subjects enrolled in the clinical study (including those withdrawn from the clinical study or lost to follow-up) shall be accounted for and documented. If a subject withdraws from the clinical investigation, the reason(s) shall be reported. If such withdrawal is due to problems related to study device safety or performance, the investigator shall ask for the subject's permission to follow his/her status/condition outside of the clinical study.

Every effort should be made to retain subject enrollment for the duration of the study. During the informed consent process, subjects should be fully informed of the data collection requirements and duration, and should only be enrolled if willing to fully participate in it.

Reasons for withdrawal may include physician discretion, subject choice to retire consent, lost to follow-up, or death. In the event a subject does decide to withdraw from the study, every effort should be made to obtain full information on any on-going reportable Adverse Events up to the point of withdrawal. Subjects should only be considered lost to follow-up after significant effort has been made to contact the subject. For subjects who are "lost-to-follow-up" the investigator/center should have at least three documented attempts to contact the subject prior to completion of the "End of Study" eCRF. Subject withdrawal and lost to follow-up will be documented on the "End of Study" electronic Case Report Form (eCRF). Additional data may no longer be collected after the point at which a subject has been withdrawn from the study or withdraws his/her consent, for whatever reason.

All open reportable Adverse Events should be closed or documented as chronic. Data collected up to the point of subject withdrawal may be used, unless any local regulations apply which require removal of the data.

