11.9. Month 3 Assessment-Ablating physician UNBLINDED to DirectSense technology

Rhythmia HDx + IntellaMap Orion will be used to collect an electroanatomic map (i.e. activation and voltage map) of the Left Atrium. In case gaps are detected and the physician decides to ablate these gaps, ablation must be performed with the IntellaNav MiFi OI catheter.

For all subjects it is preferred that all maps are acquired during pacing from the Coronary Sinus.

Gap sites will be determined for each segment and vein according to **Figure 11.5-2**. The location of each gap will be defined as a site of PV potential on the diagnostic catheter, and in the case of retreatment, to be confirmed by a change in PV activation.

The following DirectSense data has to be collected:

- Blood pool impedance measurements for approximately 10 s. In case the physician decides to ablate, this measurement has to be obtained prior to the 1st RF application (reference measurement)
- Non-ablated myocardium impedance measurements for approximately 10 s prior to the 1st RF application. In case the physician decides to ablate, this measurement has to be obtained prior to the 1st RF application (reference measurement)
- Local impedance data will be sampled approximately every 50 ms. This data will be simultaneously recorded in a digital log file by the BSC representative.

For at least 5 points that are considered as gap-free, the following DirectSense data has to be collected

• Ablated myocardium impedance measurements for approximately 10 s. In case the physician decides to ablate, this measurement has to be obtained prior to the 1st RF application (reference measurement)

For all gaps that are ablated, the following DirectSense data has to be collected:

• Gap impedance measurement for 10 s prior to first ablation within the gap

In case the ablating physician decides to ablate gaps, if any, the ablating physician can use whichever ablation technique he/she prefers. There is also no requirement to perform entrance block testing at the end of the ablation of gaps or to implement a waiting time after the ablation of gaps, if applicable. Also, there is no need to collect a Rhythmia + IntellaMap Orion activation map at the end of the ablation of gaps, if applicable.

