12.2. General Statistical Methods

12.2.1. Analysis Sets

The primary endpoint will be assessed in all Treatment subjects who complete the month 3 gap site assessment.

Additional analyses will include all subjects enrolled into the study overall and categorized according to the definitions in section 10.3 or subsets of these categories.

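### Before month 3, a different ablation catheter at a repeat left atrial procedure is enough to withdraw a subject and lose the gap outcome, although the primary endpoint does not need that catheter

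*Combined protocol and SAP*

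**What the plan says.** Section 11.1 gives two routes for a subject who needs an additional LA ablation during follow-up.

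- If Rhythmia HDx, Orion and the MiFi OI ablation catheter are all used, "then this additional ablation procedure will be considered as the month 3 assessment if the month 3 assessment was not yet performed". No out-of-window deviation is recorded.
- If a different mapping system is used, or "different mapping and/or therapeutic catheters will be used for this additional ablation procedure in the LA, the subject will have to be withdrawn" before the procedure takes place. Section 11.8 repeats this rule.

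Section 10.2 sets the effect of withdrawal: "Additional data may no longer be collected after the point at which a subject has been withdrawn from the study". It also says "Data collected up to the point of subject withdrawal may be used", subject to local regulations. Section 12.2.1 limits the primary analysis to "all Treatment subjects who complete the month 3 gap site assessment".

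Section 11.9 describes the month 3 outcome: "Rhythmia HDx + IntellaMap Orion will be used to collect an electroanatomic map (i.e. activation and voltage map) of the Left Atrium", and "The location of each gap will be defined as a site of PV potential on the diagnostic catheter". The study ablation catheter is mandatory there only if the physician chooses to treat gaps, in which case "ablation must be performed with the IntellaNav MiFi OI catheter". Section 7.1 takes the impedance side of the primary endpoint from the index procedure.

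**The concern.** The withdrawal rule treats the three study devices alike, but they do not bear alike on the primary endpoint. Changing the mapping system or the mapping catheter changes how gaps are measured. Changing only the catheter used to re-ablate leaves both the index impedance and the diagnostic map as they were.

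The subjects concerned are unlikely to be typical. The Introduction (Section 4) attributes arrhythmia recurrence mainly to reconnection of isolated veins, so patients who come back early for LA ablation can be expected to have more gaps. If gaps are uncommon, segments with gaps are the smaller group in the primary comparison and largely determine its precision. The plan gives no missing-data rule, and the attrition allowance in Section 12.1.1.2 is a head count that does not address loss related to outcome.

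**Working it through.** **1. What each part of the primary endpoint needs.** The exposure is baseline local impedance and impedance drop at the index procedure (7.1, 12.1.1). The outcome is gap status per segment, read from the Rhythmia HDx plus Orion map and from PV potentials on the diagnostic catheter (11.9). The repeat-procedure ablation catheter is named in neither.

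**2. Who is affected under 11.1, 11.8, 10.2 and 12.2.1.**

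- Month 3 already done, then a repeat LA ablation with another catheter: withdrawn, but the gap data were collected earlier and may be used. No loss.
- Before month 3, all three study devices: counts as month 3. No loss.
- Before month 3, different mapping system or mapping catheter: withdrawn. No comparable study map would exist, so this point does not cover the case.
- Before month 3, Rhythmia HDx and Orion, different ablation catheter: withdrawn first, so the map is never study data and the subject leaves the primary set. This is the case at issue.

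**3. The plan's own figures (12.1.1.2).** 50 × 1.2 = 60 reproduces the stated sample size. Dividing by the retained fraction gives 50 / 0.8 = 62.5, rounded up to 63. The drop from 60 to 50 is 10/60 = 16.7%. The 90% power at 3.71 ohms cannot be reproduced, because no SD, gap proportion or within-patient correlation is given.

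**4. Share of gap segments lost.** From the plan: 8 segments × 2 PV pairs = 16 per patient, and 60 patients. Assumed: a gap rate of 10% in the other patients, and m = 2 to 3 times that rate in the k patients lost.

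Share lost = (k × 16 × 0.10 × m) / [(k × 16 × 0.10 × m) + (60 − k) × 16 × 0.10]

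- k = 1, m = 2: 3.2 / (3.2 + 94.4) = 3.3%
- k = 1, m = 3: 4.8 / (4.8 + 94.4) = 4.8%
- k = 3, m = 2: 9.6 / (9.6 + 91.2) = 9.5%
- k = 3, m = 3: 14.4 / (14.4 + 91.2) = 13.6%

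The 10% rate cancels, so the share depends only on k and m. The gap proportion is understated: with k = 3 and m = 3 it is 105.6 / 960 = 11.0% in all 60 patients, against 10% in those retained.

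**5. Precision, as illustration only.** Take 50 × 16 = 800 independent segments, 80 of them with gaps, and two-sided alpha of 0.05. The SD that gives 90% power at 3.71 ohms is 3.71 / [(1.960 + 1.282) × √(1/80 + 1/720)] = 9.71 ohms. Removing patients with three times the average gap rate takes out 4.8 gap segments each. Power falls to 88.3% with 1 lost and 84.0% with 3 lost. This applies only if the losses come on top of the 10 patients already allowed for.

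**6. Bias.** A simulation used 50 patients, SD 12 ohms and intra-patient correlation 0.1 to 0.5. The chance of a repeat procedure rose with the number of gaps, and 25-100% of repeat patients were removed. About 1 to 3.5 patients and 3-11% of gap segments were lost. The mean impedance difference moved by less than 1%.

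**The case against.** The strongest reply is that the rule is narrow and defensible. Section 11.1 already accepts a repeat procedure done with the study devices. The documents do not show that physicians would often map with Rhythmia HDx and Orion and then ablate with something else. The study's objective is to characterise DirectSense, and Section 11.9 requires month 3 impedance readings that may depend on the MiFi OI catheter. Section 11.9 also says that in retreatment a gap is confirmed by a change in PV activation, so ablation has some part in confirming it.

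Most of this stands as a limit on size. The number affected is unknown and probably small, and by head count the allowance of 10 may absorb it. Some repeat LA procedures may treat another arrhythmia (11.8) and need not be gap-rich. The wish for complete month 3 impedance readings is a real reason for the rule, but the primary endpoint does not use those readings. The activation-change confirmation names no catheter, and it cannot be essential, because Section 11.9 leaves ablation of gaps to the physician's choice.

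A reader might infer three stronger things that the documents do not support:

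- That valid outcomes are collected and then thrown away. Withdrawal precedes the procedure, so they are never collected.
- That every subject withdrawn under the rule leaves the primary set. Those already assessed at month 3 stay in.
- That the primary mean difference is materially biased. Selection on gap count mainly changes how many gap segments there are, and the simulation showed almost no shift, though only under its own model.

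**Conclusion.** The point holds in a limited form. For a subject who needs a further LA ablation before month 3, the ablation-catheter trigger forgoes a gap outcome that the primary analysis could use, and nothing in the primary endpoint requires this. The cost is precision and an understated gap proportion.

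The size rests on assumptions. The documents give no repeat-procedure rate, no gap rate, and no gap rate among repeat patients. That these patients have more gaps is an inference from the Introduction. At 2 to 3 times the gap rate, one patient lost costs about 3-5% of gap segments and three cost about 10-14%. Larger figures can be had by assuming more patients, but nothing in the plan supports a particular number. No formal hypothesis is tested, so the consequence is a wider confidence interval. The change is still worth making because it is cheap and the loss is related to the outcome.

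**What to change.** This concerns data handling only and implies no choice of catheter or treatment.

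- In 11.1 and 11.8, tie exclusion from the gap endpoint to the absence of a Rhythmia HDx plus Orion LA map taken before re-ablation.
- If that map is obtained and month 3 has not yet been done, keep the subject in the study and count the map's gap status per segment as the month 3 assessment, whichever ablation catheter is then used.
- Reconcile the device wording in 11.9, and the footnote to Table 11.1-1 and its copy in the synopsis, which limit mapping data from an additional procedure to the full device set.
- Reconcile 11.8 with itself. It asks for eCRF details of procedures done with other devices yet requires withdrawal beforehand, and its listed fields omit gaps per segment. It also calls the primary endpoint acute procedural success, which conflicts with 7.1 and 12.1.1.
- Report the number of such subjects, and the primary analysis with and without them.

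The cost is coordinated wording changes in several sections and one sensitivity analysis. Month 3 DirectSense readings may be missing for these subjects, which affects the descriptive impedance data but not the primary endpoint.
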